Our objectives are to evaluate the effectiveness of “nudges” to clinicians, to patients, or to both in increasing in TUTS referral and engagement; and to explore clinician, patient, inner setting (e.g., clinic), and outer setting (e.g., payment structures) mechanisms related to TUTS referral and engagement. We will employ rapid-cycle approaches to optimize the framing of nudges to clinicians and patients prior to initiating the trial and mixed methods to explore contextual factors and mechanisms.

We will conduct this study with at least 100 clinicians and at least 900 smokers across Penn Medicine’s ACC (the clinician sample size may increase with additional clinicians joining Penn and the patient sample size may be higher given the pragmatic design and delay between determination of eligibility [i.e., patient smokes] and nudge delivery at a subsequent visit). We

expect the study to yield essential insights into the effectiveness of nudges as an implementation strategy to speed the uptake of high value evidence-based TUT within cancer care, and to advance our understanding of the multilevel contextual factors that drive response to these strategies. These results will lay the foundation for how cancer care settings can ensure that patients with cancer who smoke are engaged with evidence-based TUT and may lead to a future R01 focused on scaling-up this approach across other cancer centers involved in the C3I.

OBJECTIVES

Aim 1: Conduct a four-arm pragmatic cluster RCT to test the effectiveness of nudges to clinicians, nudges to patients, or nudges to both in increasing TUTS referral and engagement in cancer patients who smoke, vs. usual care (UC). H1a: Each of the implementation strategy arms will significantly increase TUTS referral and engagement compared to UC. H1b: The combination of nudges to clinicians and to patients will be the most effective.

Aim 2: Conduct a quantitative evaluation using secondary data (obtained via EMR, for patients, and by survey, for clinicians) to identify moderators of implementation effects on TUTS referral and engagement. H2: Nudge impact will be moderated by clinician, patient, and inner setting factors. [Note: the clinician survey will be conducted within a separate study funded by this grant and submitted for IRB approval as a separate protocol; data across the studies will be linked by clinician name and study ID.)

Primary outcome variables:

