6. Statistical Analysis:

Based on our preliminary data, we anticipate including at least 900 smoking patients (based on prevalence estimate of ~7% among 13,000 patients screened over a 1-year study period), nested within at least 100 clinicians. Analysis will use the first TUTS order generated for each patient/physician combination. Data are clustered within clinician, and the exchangeable correlation observed from other studies is small (0.07). We calculated power requirements by simulation using Stata 15, assuming a logistic regression model fitted using generalized estimating equations (GEE), and found our sample gives us 80% power to detect 11% improvement in our primary outcome (e.g., from current 34% referral rate to 45%), using a two-sided type 1 error rate of 5%, for planned comparisons between usual care and each individual nudge arm. The effect of the combined nudge arm is expected to be larger than each individually, indicating at least 80% power to detect probable effects for the comparison between usual care and the combined arm.

We have defined our intention to treat (ITT) sample using the coding algorithm that makes intervention possible, irrespective of whether a nudge was delivered or received. Thus, the ITT cohort is comprised of all eligible patients, defined as those who screened positive for tobacco exposure and have completed the two visits in their randomly assigned cluster. Eligible patients may or may not receive the nudge to which they were assigned and may or may not have access to MyPennMedicine; regardless, all eligible patients are analyzed in the ITT sample.

We have patient-level data on all those screened positive for tobacco but who did not complete the subsequent visits with a clinician in our cluster randomization (e.g., patient came for the first visit where the hidden system variable was assigned and never returned). While these patients are not considered eligible for our trial, they are part of the “screened” population, and we can compare them to our eligible patients on available data to assess the generalizability of our sample.

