For Aim 1, we will analyze all binary outcomes using logistic regression with GEE. The study design is factorial, and models will contain binary predictor terms for clinician and/or patient prompt. We will conduct stratified analyses by MPM access. We will also include adjustments for time in months, fixed effects for site, and random effects for clinician. We will control for type 1 error inflation by hierarchical testing, starting with the overall model significance, followed by effect of clinician prompting, followed by patient prompting. Once we have fitted the main effects model, we will test for interaction between clinician and patient prompts, and retain that interaction term if significant (alpha=5%). For Aim 2, variability in these outcomes by treatment arm and moderators will be assessed using interaction terms within logistic regression models. We will fit an adjusted logistic regression model using the same approach described in the primary analysis. Covariates of interest available through the EMR and clinician survey will be added to the model, including patient-level (e.g., cancer type), clinician-level (e.g., years in practice), practice-level (e.g., community vs. hospital-based), and ecological data.

RISK/BENEFIT ASSESSMENT:**1. Risks:**

There are minimal risks to participants in this trial. Regardless of nudges, treatment provided is FDA approved, clinicians routinely order treatment as part of their standard of care, and patients routinely use these smoking cessation treatments. The interventions could increase the time spent discussing smoking cessation with patients. However, shared-decision making is a high priority and evidence-based practice for cancer care and increased time on this topic is likely valuable. In our prior studies, nudges in the EMR were associated with minimal burden on practice staff and clinicians. There is a risk of breach of data and confidentiality, however we described the precautions in place to securely manage this data in the "Data Management" section of this protocol.

2. Benefits:

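### The type 1 error hierarchy contains none of the arm-versus-usual-care comparisons that the trial hypothesises and powers

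*Combined protocol and SAP*

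**What the plan says.** - **Objectives, Aim 1:** "H1a: Each of the implementation strategy arms will significantly increase TUTS referral and engagement compared to UC", and "H1b: The combination of nudges to clinicians and to patients will be the most effective".
- **Statistical Analysis, sample size:** 80% power at two-sided 5% to detect 34% versus 45% referral, "for planned comparisons between usual care and each individual nudge arm". It adds "at least 80% power to detect probable effects for the comparison between usual care and the combined arm".
- **Statistical Analysis, Aim 1:** "The study design is factorial, and models will contain binary predictor terms for clinician and/or patient prompt". Type 1 error is controlled by "hierarchical testing, starting with the overall model significance, followed by effect of clinician prompting, followed by patient prompting". After the main-effects fit, the clinician-by-patient interaction is tested at 5% and kept only if significant. The section does not say what becomes of the hierarchy when the interaction is kept, or how arm effects will be derived.
- **Statistical Analysis, Aim 2:** "variability in these outcomes by treatment arm and moderators will be assessed using interaction terms within logistic regression models", using the primary analysis approach, which has no arm term.
- **Background:** describes a head-to-head comparison of clinician and patient nudges. No analysis of it is specified.

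**The concern.** The hypotheses and the power statement concern arms; the error-controlled tests concern factorial main effects. The two coincide only if the nudges act additively on the logit scale, and the plan never states that assumption. As written, someone holding the final data could cite the protocol for either analysis and might get opposite answers on whether the clinician nudge works. H1b would rest on an unstated inference from two main effects. A third, conditional issue is that if main-effect coefficients are read as arm effects, as H1a requires, a low-powered pre-test decides whether those effects are estimated under additivity.

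**Working it through.** **1. What each step tests.** The main-effects model is logit(p) = b0 + bC·C + bP·P, where C and P indicate clinician and patient prompts.

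| Comparison | Additive model | With interaction bCP |
|---|---|---|
| Clinician-only vs usual care (UC) | bC | bC |
| Patient-only vs UC | bP | bP |
| Combined vs UC | bC + bP | bC + bP + bCP |
| Combined vs clinician-only | bP | bP + bCP |
| Combined vs patient-only | bC | bC + bCP |
| Clinician-only vs patient-only | bC − bP | bC − bP |

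The hierarchy tests (bC, bP) jointly, then bC, then bP, all from the additive model. Combined vs UC is a sum of coefficients and is no listed step. bC equals an arm contrast only if bCP = 0; otherwise it is an effect averaged over the other prompt.

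**2. The plan's 80%.** Inputs from Statistical Analysis: 900 patients, 100 clinicians, ICC 0.07, 34% vs 45%, two-sided 5%. Equal allocation and equal cluster size are assumed.
- Mean cluster size 900/100 = 9; design effect 1 + 8×0.07 = 1.56.
- Arm vs UC: 225/1.56 = 144.2 effective per arm. Null SE √(2×0.395×0.605/144.2) = 0.0576; alternative SE √((0.34×0.66 + 0.45×0.55)/144.2) = 0.0572. Power = Φ((0.11 − 1.96×0.0576)/0.0572) = **48%**. Ignoring clustering gives 66.6%.
- Factorial margin: 450/1.56 = 288.5 per side, power **77.3%**.

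So 80% is not reproduced for the comparison it is attached to, and lies close to the main-effect figure. The settings of the plan's simulation are not given. With the 2,300 patients and 275 clinicians of the target population, arm-level power would be 87%.

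**3. Do the two readings agree?** Simulation: beta-binomial clusters, ICC 0.07, logistic model with clinician-robust variance, no covariates, about 10,000 trials per scenario. Only 34% and 45% come from the plan; the combined rates are assumed. Additivity on the logit scale gives 56.5%. Disagreement means that exactly one of these is significant: the clinician step (overall and clinician tests) or clinician-only vs UC at unadjusted 5%. Coverage is for the clinician-only vs UC 95% CI under the retain-if-significant rule.

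| UC/clinician/patient/both (%) | Disagree, 100×9 | Disagree, 276×8 | Additive model kept, 100×9 | Coverage, 100×9 | Coverage, 276×8 |
|---|---|---|---|---|---|
| 34/45/45/56.5 | 34% | 13% | 95% | 93% | – |
| 34/45/45/53 | 28% | 12% | 93% | 90–91% | 88–89% |
| 34/45/45/50 | 26% | 13% | 88% | 86% | 78–79% |
| 34/45/45/45 | 32% | 35% | 72–73% | 77% | 71–73% |
| 34/34/34/45 | – | 53% | 72–73% | 77% | 71–73% |

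Size is clinicians × patients each; a dash means not tabulated. Under additivity at 100×9, 32 of the 34 points are trials positive only by the hierarchy (power about 77% vs 48%). At 34/45/45/45 the order reverses: about 21% vs 48%.

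**4. H1b.** Suppose two positive significant main effects with no retained interaction are read as H1b. At 34/45/45/45, where H1b is false, it is then claimed in 5% of trials at 100×9 and 13% at 276×8. Requiring the combined arm to beat both single arms gives 0.5–0.6%.

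**5. Why the interaction rule misses.** At 34/45/45/45 the interaction is −0.2007 + 2×0.2007 − 0.6633 = −0.463. Its variance is 1/(144.2×0.2244) + 3/(144.2×0.2475) = 0.0309 + 0.0841 = 0.115, so SE = 0.339, z = 1.36 and power = Φ(1.36 − 1.96), about 27–28%. When it is missed, bC is roughly the mean of the two simple effects, (0.463 + 0)/2 = 0.23, an odds ratio of 1.26 against a true 1.59. At 34/34/34/45 the rule, read as H1a, claims that clinician-only beats UC in about 17% of trials at 100×9, against 2–3% for the direct contrast. Always keeping the interaction gives 94–95% coverage throughout. At 100×9, ICCs of 0.03 to 0.12 give 74–79% under the rule at 34/45/45/45 and 85–87% at 34/45/45/50. Unequal clusters (CV 0.8) give 78% and 86%.

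**The case against.** The best defence is that the plan names one ordered procedure, that a main-effects analysis of a 2×2 factorial is standard, and that the trial is called a pilot. On that view only the wording of H1a and the power sentence is loose. Three further points have force:

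- Under additivity the disagreement is mainly a power difference between two estimates of the same log odds ratio, and it falls to 12–13% in the larger sample outside the extremes.
- The lowest coverage needs scenarios that the plan does not expect: it anticipates a larger effect of the combination, and an 11-point effect of each single nudge.
- Nothing states that arm-level intervals will come from the reduced model, or that two main effects will be taken as H1b.

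All of this limits the size of the problem. It does not remove the contradiction. If main effects were intended, H1a and the powered comparisons describe tests that will not be done. If arms were intended, they have no error control. A pilot that states significance hypotheses, power and a type 1 error scheme still has to identify its confirmatory test. The 100×9 setting is the minimum on which the power claim is based.

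**Conclusion.** The concern holds and must be resolved before analysis. Followed as written, the plan has no error-controlled test of any arm against usual care and no explicit test of H1b. At the stated minimum size the two candidate primary analyses disagree in roughly a quarter to a third of trials, and which is more favourable depends on the unknown combined-arm rate. The severity rests on this point. The H1b and interaction-rule findings are conditional: they matter to the extent that effects are not additive and coefficients are read as arm effects. Coverage then ranges from 90–91% (combined rate 53%) to about 77% (45%) at 100×9, and a larger sample does not cure it. The figures assume equal arms, ICC 0.07, no site or time adjustment, and the combined-arm rates shown.

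**What to change.** Drop the retain-if-significant rule for arm-level estimates. From a model that always contains the interaction (equivalently, four arm indicators), report with CIs the four arm rates, each nudge arm vs UC, combined vs each single arm, and clinician-only vs patient-only. Then declare one confirmatory family.

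- **Option A, arm contrasts.** For example, Holm over the three arm-vs-UC p-values plus one for H1b. The H1b p-value is the larger of the two combined-vs-single p-values if both differences favour the combination, and 1 otherwise. The direction is needed: at 34/45/45/34 the larger two-sided p-value is below 0.05 in 32% of trials. Restate the power to match.
- **Option B, main effects.** Keep the present hierarchy, restate H1a and the power as main effects, state the additivity assumption, and label H1b and all arm contrasts descriptive.

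Under either option, say which terms Aim 2 means by treatment arm.

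No new data are needed. The cost is wider arm-level intervals (SD of a single-arm risk difference 5.7 points, against 4.0 in the additive model) and lower stated power. At 100×9 under additivity:

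- **Option A:** each single arm vs UC 35% (48% unadjusted), combined vs UC 91%, H1b 21–22% (33% unadjusted).
- **Option B:** 78% per main effect, but 61–62% for patient prompting because it is tested last. Per-effect power falls to 50% at 34/45/45/50 and 27% at 34/45/45/45, and there is no confirmatory answer on H1b.

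Clinician-only vs patient-only has a 95% CI of about ±11 points at this size, so it is descriptive under both options.
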